**Co-Investigators:**  
**[name]**  
**[name]**  
**[name]**  
**[name]**

Department of Hematology

Division of Anesthesiology

Department of Biostatistics

St. Jude Children's Research Hospital  
[name]  
[name]  
[contact]

PMVOC - Pain Management of Vaso-occlusive Crisis in Children and Young Adults with Sickle Cell Disease
Principal Investigators: [name] and [name]
IND Holder: St. Jude Children's Research Hospital, # 119125
Brief Overview: This is a phase II double-blind placebo-controlled clinical trial evaluating the effect of gabapentin when added to standard pain management for patients with sickle cell disease experiencing acute pain crisis in the ambulatory care setting. Patients will be randomized to receive a single oral dose of gabapentin or placebo as soon as feasible after enrollment. Pain scores and opioid requirement will be measured and compared across treatment arms, along with the outcomes of discharge from clinic versus admission to the inpatient unit.
Intervention: Gabapentin 15mg/kg vs placebo (single dose by mouth)
Brief Outline of Treatment Plan: Participants will receive a single dose of study drug by mouth as soon as feasible after enrollment, while standard pain management is provided concurrently. The remainder of care for the painful event will continue per institutional standards according to clinical indication, including reassessment and documentation of pain and additional doses of pain medicines by IV or oral route. Treating clinicians will determine if the patient may be discharged home or if admission is warranted.
Study Design: Phase II double-blind placebo-controlled therapeutic trial.
Sample Size: 166 participants divided evenly between active and placebo arms.
Data Management: Data management and statistical analysis will be provided locally by the Anesthesia Division and Biostatistics Department at St. Jude Children's Research Hospital
Human Subjects: The risks to subject will be related to the toxicity of gabapentin. The expected side effect is somnolence. Patients will be informed of this and other minor side effects during informed consent discussion. Adverse events will be monitored and reported and treated appropriately.

## Appendices

Appendix I: Schedule of Evaluations

Appendix II: Tests Performed for Good Clinical Care

Appendix III: Recruitment Materials

Appendix IV: Gabapentin Drug Formulation

Appendix V: Gabapentin Placebo Drug Formulation

## 1.0 **OBJECTIVES**

### 1.1 **Primary Objective**

To assess the analgesic efficacy of gabapentin (vs. placebo) for pain during vaso-occlusive crisis (VOC) in participants with sickle cell disease (SCD). A response to study drug will be defined by a decrease in pain score of  $\geq 33\%$  between presentation to the acute care setting and assessment at 3 hours post administration of study drug.

[figure not shown]
### 1.2 **Secondary Objective**

To compare the total morphine equivalent dose (mg/kg) used to control pain during VOC between presentation to the acute care setting and assessment at 3 hours post administration of study drug in the gabapentin vs. placebo groups.

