### 1.3 **Exploratory Objectives**

- 1.3.1 To assess the analgesic efficacy of gabapentin (vs. placebo) for pain during VOC in participants with SCD, as defined by a decrease in pain scores of  $\geq 33\%$  between presentation to the acute care setting and the point of decision for either hospital admission or discharge to home, in the gabapentin and placebo groups.
- 1.3.2 To compare the total morphine equivalent dose (mg/kg) used to control pain during VOC between presentation to the acute care setting and the point of decision for either admission or discharge to home, in the gabapentin and placebo groups.
- 1.3.3 To compare the rate of admission related to pain management, in the gabapentin vs. placebo groups.
- 1.3.4 To compare the change in pain score from time of administration of study drug to assessment at 3 hours post administration of study drug in the gabapentin vs. placebo groups.
- 1.3.5 To compare the change in pain score from time of administration of study drug to the point of decision for either admission or discharge to home, in the gabapentin and placebo groups.

Figure 1. Pain Assessment Time Points and Study Objectives

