## **4.0 TREATMENT PLAN**

### **4.1 Treatment**

Upon each participant’s enrollment, study staff will randomize the participant to one of 2 possible treatment arms (see section 11 for randomization procedure) and order the study treatment. The pharmacy will dispense the dose of study treatment ( gabapentin vs. placebo) to the clinic or medicine room as soon as possible.

Study drug and other interventions will be administered and documented according to hospital policy by any appropriate clinical staff. All caregivers and study personnel will be blinded to the treatment assignment. Based on previous research experience at St. Jude, administration of the study drug is estimated to occur no later than 2 hours after patient’s first opioid pain medication in the acute care setting.

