#### **4.3 Concomitant Therapy**

It is expected that participants in this study may be receiving concomitant therapies unrelated to the primary interests of this study. Only the study treatment and IV administered pain control treatments will be analyzed to determine the study outcomes. Patients on long-term treatments for sickle cell disease (e.g. hydroxyurea or chronic transfusion therapy) will be recorded for analysis.

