## 11.2 Randomization

Eligible patients with an established diagnosis of pain and VOC will be consented and randomized to receive a single dose of gabapentin or placebo. Morphine or other opioid and non-steroidal anti-inflammatory drugs will be available to both groups as needed for pain and will be administered according to the current standard of care for pain in VOC from the Department of Hematology. Randomization will be performed in SJCRH pharmacy by a pharmacist, using the randomization program developed by the Department of Biostatistics. The randomization will be stratified by three age categories (1-3yr, 4-6yr,  $\geq 7$ yr) for which distinct pain assessment tools are applied and for 2 pain scores categories at assessment at presentation: 4- 6 and 7-10, respectively. A

block randomization with block sizes varying randomly between 4 and 6 will be used in each stratum.

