#### **11.3.2 Secondary Objective**

To compare the total morphine dose or morphine equivalent (mg/kg) used to control pain during VOC between presentation to the acute care setting and assessment at 3 hours post administration of study drug in the gabapentin vs. placebo groups.

Summary statistics of the total morphine dose or morphine equivalent (mg/kg) used to control pain during VOC between presentation to the acute care setting and 3 hours post administration of study drug, in the gabapentin and placebo groups will be provided. Test of normality such as Shapiro-Wilk test will be applied to the total morphine dose or morphine equivalent (mg/kg) to examine their deviation from the normal distribution. A two-sample t-test or Wilcoxon rank sum test will be used to compare the total morphine dose or morphine equivalent (mg/kg) for the gabapentin vs. placebo groups depending on whether the normality assumption of the data holds.

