## APPENDICES

### APPENDIX I: Schedule of Evaluations (**required**)

Event	Screen 	Entry	On Treatment			24-72 hours after study drug
			Acute care setting	3 hours after study drug	Decision to discharge from acute care or admit	
Informed Consent	X					
Pregnancy test	PRN					
Pain assessment	X	X 	PRN	X	X 	
Study drug		X				
Pain intervention	PRN	PRN	PRN	PRN		
Adverse event screen				X	X	X
Off study						X

Routine pain interventions may begin before study entry/administration of study drug

Patients who leave the ACU at the 3 hour time point will not have a fourth pain assessment captured

Pain score will be recorded within 30 minutes of drug administration.

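### The secondary opioid total includes opioid given before study drug, and the planned unadjusted comparison can lose precision that adjusting for the pre-drug amount would recover at almost no cost

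*Combined protocol and SAP*

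**What the plan says.** Section 1.2 sets one secondary outcome: the total morphine equivalent dose in mg/kg, accumulated "between presentation to the acute care setting and assessment at 3 hours post administration of study drug in the gabapentin vs. placebo groups". Exploratory objective 2 (section 1.3.2) also starts at presentation and runs to the decision to admit or discharge.

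Opioid can come before study drug. Appendix I, note 1: "Routine pain interventions may begin before study entry/administration of study drug". Section 4.1 adds that "administration of the study drug is estimated to occur no later than 2 hours after" the first opioid in the acute care setting. That is an expectation, not a limit.

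Section 11.3.2 gives the analysis: "A two-sample t-test or Wilcoxon rank sum test will be used to compare the total morphine dose or morphine equivalent", with the choice resting on a test of normality. It names no covariate. Randomization is stratified by three age groups and "for 2 pain scores categories at assessment at presentation" (section 11.2), but the strata do not enter this comparison. Section 11.3.3 applies the same methods to exploratory objective 2.

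The protocol does use a window that starts at dosing, but only for pain. Objective 1.3.4 reads: "To compare the change in pain score from time of administration of study drug to assessment at 3 hours post administration of study drug". No opioid analysis starts at study drug.

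**The concern.** The total is the sum of a part given before dosing, which the drug cannot change, and a part given after it. The first part also depends on how long consent, randomization and dispensing take. An unadjusted test carries the variation of both parts, although the treatment effect can lie only in the second.

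Opioid sparing is central to the rationale in section 2.1, this is the sole secondary outcome, and no power is stated for it. If the pre-drug part varies a good deal, the interval for the mg/kg difference will be wider than the data require, and a null result will be harder to interpret. The pre-drug amount is measured before treatment, so it is a legitimate covariate and can be derived from records already being abstracted.

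**Working it through.** **The plan's own figure.** The documents give no standard deviation, effect size or power for the opioid outcome. The only sample size is the primary one, and it reproduces. With 45% vs 65%, an interim at 96/166 = 0.578 of the information, and nominal one-sided p-values of 0.0143 (efficacy), 0.2249 (futility) and 0.0447 (final), the type I error is 0.0500 with futility ignored. Power at 166 is 80.1% with futility obeyed, and 166 is the smallest even total that reaches 80%. Nothing below changes this.

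**Timing.** Two hours from first opioid to study drug (section 4.1, estimated maximum) plus 3 hours after it is 5 hours. So up to about 2 of 5 opioid-exposed hours may precede dosing.

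**Efficiency.** Scale the post-drug SD to 1. Let k = SD(pre)/SD(post) and rho = the within-arm correlation of the two parts. Both are assumptions.

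- Variance of the unadjusted total: 1 + k² + 2·rho·k.
- Residual variance after adjusting for the pre-drug amount: 1 − rho².
- Relative efficiency RE = (1 − rho²)/(1 + k² + 2·rho·k).

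The denominator minus the numerator is (k + rho)². So the unadjusted total never beats adjustment (apart from one degree of freedom), and it loses nothing exactly when rho = −k.

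Example, k = 0.5 and rho = 0.3: RE = 0.91/(1 + 0.25 + 0.30) = 0.91/1.55 = 0.59. The equivalent sample size is 166 × 0.587 = 97. If the adjusted analysis had 80% power (two-sided 0.05), the unadjusted total would have Φ(2.80 × √0.587 − 1.96) = 57%.

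| k | rho | RE | Equivalent N of 166 | Power when adjusted has 80% |
|---|---|---|---|---|
| 0.25 | 0.5 | 0.57 | 95 | 56% |
| 0.25 | 0.3 | 0.75 | 125 | 68% |
| 0.25 | 0 | 0.94 | 156 | 78% |
| 0.25 | −0.3 | 1.00 | 166 | 80% |
| 0.5 | 0.5 | 0.43 | 71 | 45% |
| 0.5 | 0.3 | 0.59 | 97 | 57% |
| 0.5 | 0 | 0.80 | 133 | 71% |
| 0.5 | −0.5 | 1.00 | 166 | 80% |
| 1 | 0.5 | 0.25 | 42 | 29% |
| 1 | 0.3 | 0.35 | 58 | 38% |
| 1 | 0 | 0.50 | 83 | 51% |
| 1 | −0.3 | 0.65 | 108 | 62% |

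**Simulation check** (83 per arm, 3,000 runs per scenario). Power of the t-test / Wilcoxon test on the total, where the adjusted analysis has about 80%:

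- k = 0.5, rho = 0: 70% / 68%
- k = 0.5, rho = 0.3: 57% / 56%
- k = 0.5, rho = −0.5: 80% / 78%

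These agree with the formula. I confirmed the pattern with normally distributed amounts; for skewed data the figures are a guide only.

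**Window or adjustment?** Because total = pre + post, regressing the total on arm and pre-drug amount gives the same treatment estimate as regressing the post-drug amount on them. So the missing adjustment matters, not the stated window. Restricting to post-drug opioid without adjustment is not always better: at k = 0.5, rho = −0.5 it has 68% power, against 80% for the total.

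**Dilution.** If a share f of the opioid in the placebo group precedes dosing, a post-drug reduction d appears as (1 − f)·d of the total. With f = 40% and d = 35% (both assumed for illustration), 0.6 × 35% = 21%.

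**The case against.** The total over this interval is a coherent companion to the primary endpoint, which also runs from presentation to 3 hours after study drug. The authors knew of the dosing-based window, since objectives 1.3.4 and 1.3.5 use it. This stands, and it is a reason to keep the total. It is not a reason to leave it unadjusted.

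The size of the loss is open. Two hours is an expected maximum, and dosing is meant to be as soon as feasible. If variance grew in proportion to time (an assumption), a 2-hour delay gives k = √(2/3) = 0.82 and a 1-hour delay k = √(1/3) = 0.58. At 1 hour, RE is 0.54 to 0.92 for rho from 0.3 to −0.3. Negative rho is possible, since more opioid early may mean less later. With fairly uniform early dosing (k = 0.25, rho from −0.3 to 0) the loss is only 0% to 6%. This also stands.

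Several stronger readings are tempting, and the documents support none of them:

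- That much of the precision is certainly lost, or that a true opioid-sparing effect will probably be missed. Both need SDs, a correlation and an effect size that are not given.
- That the comparison is biased. Assignment is randomized and blinded, so the expected pre-drug amount is equal between arms.
- That pre-drug opioid is nothing but noise. Where rho is not zero it is prognostic, which is part of why adjustment helps.
- That the normality pretest is itself a fault. In simulation at 83 per arm, skewed data went to the Wilcoxon test in 99% to 100% of runs, so the pretest alone does little harm.

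**Conclusion.** The point holds as an avoidable loss of precision of uncertain size. The total includes opioid that treatment cannot affect, and nothing in the plan adjusts for it or analyses opioid from dosing onward. The loss of information is 0% to 75% over k from 0.25 to 1 and the values of rho shown. It is about 20% to 75% if pre-drug opioid varies at least half as much as post-drug opioid and the two are uncorrelated or positively correlated (up to 0.5). It is negligible when rho is near −k. Any percentage reduction is understated relative to the post-drug effect; the mg/kg difference is not. This is an unpowered secondary outcome in a phase II trial, so the change is a free improvement, not a correction on which the trial depends.

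**What to change.** Keep the total as defined, and change its prespecified comparison in section 11.3.2 to an ANCOVA on the mg/kg scale. Adjust for morphine equivalent (mg/kg) given from presentation to study drug, counted by the same rules as the total, and for the randomization strata. If the data are skewed, use robust or bootstrap intervals. Add rank ANCOVA as a sensitivity test only, because it gives no mg/kg difference. Avoid a log scale: zero amounts are possible, since section 4.3 states "Only the study treatment and IV administered pain control treatments will be analyzed to determine the study outcomes", so a participant given only oral opioid could count as zero.

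Opioid from study drug to 3 hours may be reported alongside, also adjusted for the pre-drug amount. Apply the same approach to exploratory objective 2.

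The cost is a change of wording in section 11.3 and splitting the abstracted opioid record at the dosing time. No visit, clinical procedure or sample size changes. The change should be made before unblinded data are seen.

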### 1.3 **Exploratory Objectives**

- 1.3.1 To assess the analgesic efficacy of gabapentin (vs. placebo) for pain during VOC in participants with SCD, as defined by a decrease in pain scores of  $\geq 33\%$  between presentation to the acute care setting and the point of decision for either hospital admission or discharge to home, in the gabapentin and placebo groups.
- 1.3.2 To compare the total morphine equivalent dose (mg/kg) used to control pain during VOC between presentation to the acute care setting and the point of decision for either admission or discharge to home, in the gabapentin and placebo groups.
- 1.3.3 To compare the rate of admission related to pain management, in the gabapentin vs. placebo groups.
- 1.3.4 To compare the change in pain score from time of administration of study drug to assessment at 3 hours post administration of study drug in the gabapentin vs. placebo groups.
- 1.3.5 To compare the change in pain score from time of administration of study drug to the point of decision for either admission or discharge to home, in the gabapentin and placebo groups.

Figure 1. Pain Assessment Time Points and Study Objectives

## 2.0 BACKGROUND AND RATIONALE

### 2.1 Background:

Gabapentin has been used successfully to treat neuropathic pain [1-3], and nociceptive pain [4]. The mechanism of action is binding of the  $\alpha$ -2- $\delta$  subunits of the voltage-dependent calcium ion channels, which blocks the development of hyperalgesia and central sensitization [5, 6]. The reasons for the effectiveness of gabapentin for nociceptive pain are based on several considerations:

1. Gabapentin has been shown to prevent central sensitization, manifested as hyperalgesia, a known phenomenon in postoperative pain [7]. The mechanism for reduction of central sensitization is the reduction of hyperexcitability of secondary nociceptive neurons in the dorsal horn, through suppressing the release of excitatory amino acids in the spinal cord in response to noxious stimuli [8].
2. Gabapentin and morphine may be synergistic due to separate actions on the peripheral and central nervous system [9].
3. Gabapentin may decrease the postoperative morphine requirement by preventing the development of opioid tolerance [10].

Sixteen randomized controlled trials were included in a systematic review of gabapentin use for postoperative pain [4].

Among three different gabapentin regimens including a single dose of 1200 mg preoperatively, a <1200 mg single dose preoperatively, multiple doses perioperatively (both preoperatively and postoperatively), the regimens of single doses of 1200 mg or less were found effective by two measures of analgesic efficacy: 1) reduced pain intensity scores, and 2) reduced opioid consumption for the first 24 hours postoperatively. The single dose regimen of 1200 mg also prolonged the time to first request for rescue analgesia with opioid.

In a randomized controlled study of gabapentin 15 mg/kg single dose versus placebo in children aged 9 to 18 years undergoing spinal fusion surgery, the investigators found a significant decrease in the total morphine consumption in the gabapentin group, in the recovery room, and at postoperative day 1 and 2 [11]. The pain scores were also significantly decreased in the gabapentin group in the

recovery room and at postoperative day 1. In this study, gabapentin versus placebo was administered postoperatively for 5 days, at doses of 5 mg/kg TID; the analgesic benefit of gabapentin was only found for the first 2 days postoperatively based on diminished opioid consumption and only for the first postoperative day based on both decreased opioid consumption and decreased pain scores. The authors concluded that perioperative use of gabapentin seems to be an effective adjunct to improve pain control and is recommended as an initial loading dose of gabapentin and continued treatment for 2 days after spinal fusion surgery.

The current algorithms for management of pain associated with VOC in SCD are not satisfactory. The most effective pain treatment should intervene early in the course of a VOC, in the prodromal phase; early intervention could prevent or minimize tissue damage [12]. If we can demonstrate that a therapeutic intervention with a single dose of gabapentin can provide analgesic efficacy, this drug could be utilized as an early intervention, which can be initiated at home, in the prodromal phase of a VOC.

In addition to ample evidence of efficacy for management of neuropathic pain, gabapentin has proven opioid-sparing effects in an acute pain setting, that of acute postoperative pain, in adults [13, 14] and children [11]. The regimen applied in the pediatric postoperative setting, in children 9 to 18 years, was gabapentin 15 mg/kg versus placebo, given preoperatively. After surgery, the regimen continued as 5 mg/kg or placebo 3 times a day for 5 days. This regimen of an initial preoperative loading dose and continued oral gabapentin postoperatively decreased the total morphine consumption and pain scores up to 2 days postoperatively, but no benefit was demonstrated beyond 2 days.

*Additional Literature review of gabapentin for acute postoperative pain*

*Cochrane review*

A Cochrane review has evaluated the single oral dose, randomized, double-blind, placebo-controlled trials of gabapentin for relief of established moderate to severe postoperative pain in adults (>15 yrs) [15]; the dose evaluated in the review was a 250 mg single dose administered preoperatively. Studies were assessed for methodological quality and data extracted by two review authors independently. Numbers of participants with at least 50% of maximum possible total pain relief (TOTPAR) or summed pain intensity difference (SPID) with gabapentin or placebo were calculated and used to derive relative benefit (RB) or risk (RR), and number-needed-to-treat-to-benefit (NNT). Numbers of participants using rescue

medication, and time to its use, were sought as additional measures of efficacy. Information on adverse events and withdrawals was collected. Four unpublished studies met inclusion criteria; in three, participants had pain following dental surgery, and one followed major orthopedic surgery; 177 participants were treated with a single dose of gabapentin 250 mg, 21 with gabapentin 500 mg, and 172 with placebo. At least 50% pain relief over 6 hours was achieved by 15% with gabapentin 250 mg and 5% with placebo; giving a RB of 2.5 (95% CI 1.2 to 5.0) and an NNT of 11 (6.4 to 35). Significantly fewer participants needed rescue medication within 6 hours with gabapentin 250 mg than with placebo; NNT to prevent use 5.8. About one third of participants reported adverse events with both gabapentin 250 mg and placebo. No serious adverse events occurred with gabapentin. The authors' conclusions were that gabapentin 250 mg is statistically superior to placebo in the treatment of established acute postoperative pain, but the NNT of 11 for at least 50% pain relief over 6 hours with gabapentin 250 mg is of limited clinical value and inferior to commonly used analgesics. Gabapentin 250 mg is not clinically useful as a stand-alone analgesic in established acute postoperative pain, though this is probably the first demonstration of analgesic effect of an antiepileptic in established acute pain.

**Table 1.** Summary of results of gabapentin for surgical pain presented by Straube, et al in a Cochrane Review, 2010, page 8 [15]

Summary of results: gabapentin 250 mg versus placebo				
Outcome	Studies	Gabapentin (%)	Placebo (%)	Summary statistic
Number of participants with $\geq 50\%$ pain relief over 6 hours	3	15	5	NNT: 11 (6.4 to 35)
Number of participants using rescue medication over 6 hours	3	68	86	NNTp: 5.8 (3.8 to 12)
Number of participants with $\geq 1$ adverse event	3	28	32	NNH: not calculated

Based on the evidence that low dose gabapentin (250 mg, approximately 3-5mg/kg in adults) has limited efficacy, we propose a higher dose regimen in our study intervention, at 15 mg/kg, maximum 900 mg.

*Meta-analyses and systematic reviews*

Three meta-analyses [16-18] and one systematic review [4] provide reviews of placebo controlled RCTs of the use of gabapentin for perioperative pain control in adults. The systematic review [4] included 16 RCTs in the analysis. A total of 1151 patients were studied, of whom 614 patients received gabapentin. Gabapentin was given as a single preoperative dose in 11 [13, 19-27], as two separate preoperative doses in 1 [28], and as more than two doses in the perioperative period in four clinical trials [14, 29-31]. The dosages of gabapentin administered ranged between 300 and 1200 mg. To facilitate quantitative analysis, three subgroups were created: (i) group receiving single dose of gabapentin 1200 mg preoperatively; (ii) group receiving single dose of gabapentin less than 1200 mg preoperatively; and (iii) group receiving multiple doses of gabapentin in the perioperative period. Pain intensity, total analgesic consumption and time to first request for rescue analgesia were analyzed separately in each subgroup.

Eight trials used a single preoperative dose of 1200 mg gabapentin in the treatment group [13, 19, 22, 24-27, 32] Combined data on pain intensity in six studies [13, 21, 22, 25-27, 32] showed a significant decrease in pain intensity at rest with gabapentin compared with control in the early by weighted mean differences (WMD, -16.55 mm; 95% CI -25.66 to -7.44) and late (WMD, -10.87 mm; 95% CI -20.90 to -0.84) postoperative period at 6 and 24 h, respectively. Combined data from three studies that reported on opioid consumption at 24 h [13, 22, 24] showed that the WMD of -27.9 mg (95% CI -31.52 to -24.29) was in favor of gabapentin. Meta-analysis of the two studies with data on the time to first request for rescue analgesic [13, 32] showed that gabapentin produced a statistically significant delay in time to first request for analgesia (WMD 7.42 min; 95% CI 0.49–14.34).

Five studies with seven treatment arms used a single preoperative dose of gabapentin that was less than 1200 mg [20-23, 27]. The dose range was between 300 and 900 mg. Combined data from all five RCTs showed a statistically significant decrease in pain intensity at rest with gabapentin compared with control in the early postoperative period at 6 h (WMD, -22.43 mm; 95% CI -27.66 to -17.19). Combined data from four RCTs [20-23] showed lower pain scores at rest in the gabapentin group in the late postoperative period at 24 h (WMD, -13.18 mm; 95% CI -19.68 to -6.68). Combined data from four RCTs [20-23] showed that gabapentin reduced postoperative morphine consumption compared with control (WMD, -15.98 mg; 95% CI -23.45 to -8.50). None of the five studies measured time to first analgesia as an outcome.

Five studies reported gabapentin given as multiple doses perioperatively. Gabapentin was administered as follows in these five studies: 1) two separate 400 mg doses preoperatively [28]; 2) 600 mg 1 h preoperatively and then three times a day for 24 h postoperatively [30]; 3) 1200 mg of gabapentin before surgery followed by 600 mg 8 hourly for an additional three doses [29]; 4) 400 mg gabapentin the night before surgery and then 400 mg three times a day for 10 days [14]; and 5) 1200 mg gabapentin preoperatively, followed by 1200 mg on the morning of the first and second postoperative day [31]. Only two out of the five trials had data suitable for meta-analysis for the pain intensity outcome measure [14, 30]; the combined data did not show any difference between gabapentin and control groups at both 6 and 24 h after surgery. Only one study measured 24 h morphine consumption as an outcome [31]: it showed a 24% reduction in total patient-controlled analgesia morphine usage in the gabapentin group compared with the control group. Only one study presented the time to first request for rescue analgesic data as an outcome and reported no difference between the gabapentin and control groups [14].

This systematic review demonstrated that preoperative gabapentin administration was useful for postoperative pain management. A single preoperative dose of gabapentin, 1200 mg or less, effectively reduced pain intensity and opioid consumption for the first 24 h after surgery. In the subgroup that received a single 1200 mg of gabapentin preoperatively, the time to first request for rescue analgesia was also prolonged. However, multiple dosing with gabapentin preoperatively and continued postoperatively did not appear to reduce VAS pain scores.

This systematic review therefore demonstrates a potential role for preemptive gabapentin as an adjunct to standard postoperative pain management. In the groups receiving a single dose of gabapentin preoperatively, the reduction in pain scores appeared to be more pronounced in the early postoperative period. However, this reduction was still significant at 24 h and was associated with a significant reduction in opioid consumption.

The conclusion of the systematic review was that perioperative administration of gabapentin is effective in reducing pain scores, opioid requirements and opioid-related adverse effects in the first 24 h after surgery. Sedation was associated with its use but no serious adverse effects were observed.

One meta-analysis [18] evaluated eighteen studies [13, 14, 19-34] encompassing 1181 patients; mean ages ranged from 29 to 52 years of age. The most common

dose of gabapentin assessed was 1200 mg daily (12 studies), with some studies using doses as low as 300 mg daily (Table 2). Eleven studies [13, 19-27, 32] administered gabapentin as a single dose within 1 h to 2 h before surgery; the remainder involved initiating therapy on the day before surgery or continuing it for up to 10 days after surgery (Table 2). Gabapentin caused a significant reduction in postoperative pain at rest [13, 14, 19-31, 33, 34] in the first 24 h, by 27% to 39% (7.2 mm to 14.3 mm on a scale of 0 mm to 100 mm), regardless of whether treatment effects were expressed as ratios of means or weighted mean differences. Similarly, aside from 24 h after surgery, gabapentin significantly reduced pain with movement [13, 14, 19, 20, 25, 28-30, 33] by 18% to 28% (VAS 8.2 mm to 10.2 mm) after surgery. Fourteen studies [14, 19, 20, 22, 23, 25-27, 33], encompassing 1027 participants, reported effects on cumulative 24 h analgesic consumption. Gabapentin resulted in a 35% reduction in total analgesic consumption over the first 24 h following surgery (ratio of means 0.65, 95% CI 0.59 to 0.72;  $P<0.001$ ), albeit with significant heterogeneity ( $I^2=84.4\%$ ). The data on time to first analgesic was available in three studies [13, 24, 32], (171 patients); it was delayed 7.9 min by gabapentin (95% CI 4.2 to 11.6;  $P<0.001$ ), with minimal heterogeneity ( $I^2=0\%$ ).

This meta-analysis concluded that perioperative administration of gabapentin reduces pain scores, both at rest and with movement following various surgeries, lengthens the time for analgesic rescue, decreases the consumption of opioids and lowers rates of opioid-related side effects. The pain score at rest was reduced by 27% to 39% (VAS 7.2 mm to 14.3 mm on a scale of 0 mm to 100 mm) during the first 24 h, and the pain score with movement was reduced by 18% to 28% (VAS 8.2 mm to 10.2 mm) in the first 12 h.

The two meta-analyses on the topic of perioperative use of gabapentin published prior to Peng's meta-analysis of 18 studies were less extensive and included only eight [16], and 12 [17] studies, respectively; therefore they are not included in this literature review.

The evidence of effectiveness of gabapentin as an adjunct to reduce acute postoperative pain has further generated the question of whether gabapentin would also be effective in preventing chronic post-surgical pain. A recent combined systematic review and meta-analysis reviewed the effectiveness of gabapentin and pregabalin in the perioperative period for the prevention of chronic post-surgical pain [35] and concluded that perioperative administration of gabapentin and pregabalin is effective in reducing the long-term incidence of chronic post-surgical pain.

**Table 2.** Characteristics of the studies included in the Peng (2007) meta-analysis

Study	Procedure	n	Treatment arm	Control arm	Anesthesia
Gynecological procedures					
Dierking et al (34)	Abdominal hysterectomy	80	Gabapentin 1200 mg 1 h before surgery, and 600 mg 8 h, 16 h and 24 h after initial dose	Placebo	General
Gilron et al (35)	Abdominal hysterectomy	52	Gabapentin 1800 mg daily starting 1 h before surgery to postoperative day 2	Placebo	General
Rorarius et al [32]	Vaginal hysterectomy	90	Gabapentin 1200 mg 150 min before surgery	Oxazepam 15 mg	General
Turan et al [25]	Abdominal hysterectomy	50	Gabapentin 1200 mg 1 h before surgery	Placebo	General
Turan et al [34]*	Abdominal hysterectomy	50	Gabapentin 1200 mg daily starting 1 h before surgery to postoperative day 2	Placebo	General
Yoon et al [33]	Abdominal hysterectomy	32	Gabapentin 800 mg before surgery (400 mg the night before surgery and 400 mg 30 min before surgery)	Placebo	General
Orthopedic procedures					
Menigaux et al [13]	Knee surgery	40	Gabapentin 1200 mg 2 h before surgery	Placebo	General
Pandey et al [21]	Spine surgery	56	Gabapentin 300 mg 2 h before surgery	Placebo	General
Pandey et al [22]	Spine surgery	100	Any of four doses of gabapentin (300 mg, 600 mg, 900 mg or 1200 mg) 1 h before surgery	Placebo	General
Radhakrishnan et al [28]	Spine surgery	60	Gabapentin 800 mg before surgery (400 mg the night before surgery and 400 mg 2 h before surgery)	Placebo	General
Tuncer et al [27]	Major orthopedic surgery	45	Any of two doses of gabapentin (800 mg or 1200 mg) 1 h before surgery	Placebo	General
Turan et al [24]	Spine surgery	50	Gabapentin 1200 mg 1 h before surgery	Placebo	General
Turan et al [31]	Lower limb surgery	40	Gabapentin 1200 mg daily starting 1 h before surgery to postoperative day 2	Placebo	General & epidural
Other procedures					
Dirks et al [19]	Breast surgery	70	Gabapentin 1200 mg 1 h before surgery	Placebo	General
Fassoulaki et al [14]†	Breast surgery	50	Gabapentin 1200 mg daily starting evening before surgery to postoperative day 10	Placebo	General
Pandey et al [20]	Laparoscopic cholecystectomy	206	Gabapentin 300 mg 1 h to 2 h before surgery	Placebo	General
Pandey et al [23]	Open nephrectomy	60	Gabapentin 600 mg either 2 h before surgery or following surgical incision.		
Turan et al [26]	Ear-nose-throat surgery	50	Gabapentin 1200 mg 1 h before surgery	Placebo	Sedation

\*Additional two arms that assessed celecoxib (alone and in conjunction with gabapentin) were excluded; †Additional arm that assessed mexilitene was excluded

*Other RCTs of gabapentin in the perioperative period (2010-2013)*

Clinical studies with a RCT design, published recently (2010-2013) and not included in any previous meta-analyses or systematic reviews, are presented in Table 3. Of 20 RCTs, 16 found a positive outcome for at least one outcome measure, while 4 studies had negative or inconclusive results. The only pediatric study [11] is also included in Table 3.

Based on the comprehensive literature review, which is suggestive of the efficacy of gabapentin for nociceptive acute postoperative pain, we propose that the nociceptive pain encountered in the VOC crisis could also be responsive to the addition of gabapentin to the other two classes of medications representing the current standard of care, opioids and non-steroidal anti-inflammatory drugs.

Based on evidence that a single dose regimen has better analgesic efficacy than multi-dose regimens, we proposed a single dose of gabapentin of 15mg/kg, maximum 900mg.

Table 3. Randomized Controlled Trials investigating gabapentin for surgical pain, 2010 – 2013.

Author, Year [Reference]	n (analyzed)	Population	Intervention	Outcome measure	Results	
Paul, 2013 [36]	101	Total Knee Arthroplasty, adults	PBO vs Gaba 600mg preop + 200mg q8h x2d	Cumulative morphine consumption at 72h; pain scores and pt satisfaction	-	No effect on morphine consumption; No effect on pain scores or pt satisfaction
Clarke, 2013 [37]	50 (44)	Adult females with anxiety + surgery	PBO vs Gaba 1200 preop	Reduction in preop anxiety	+	gabapentin prior to surgery reduces preoperative anxiety scores and pain catastrophizing scores and increases sedation prior to entering the operating room.
Lee, 2013 [38]	80 (71)	Elective thyroid surgery, adults	PBO vs Gaba 600mg preop	Reduction of incidence of postop sore throat at rest and during swallow; Reduction of intensity of postop sore throat at rest and during swallow	+	gaba reduced sore throat incidence and intensity at rest, but not during swallow.
Short, 2012 [39]	132 (126)	Elective cesarean delivery, adult women	PBO vs Gaba 600mg preop vs Gaba 300mg preop	Pain on movement at 24h; pt satisfaction, supplemental opioid, other endpoints related to childbearing	none	Results did not reach statistical significance, insufficient power to detect difference
Adam, 2012 [40]	64	Surgery under GA, adults	PBO vs Gaba 1200mg	Reduction of preop anxiety; preop sedation without amnesia	+	Statistically significant decrease of one anxiety measure, decrease (not stat sig) of second anxiety measure. No significant differences in sedation or memory or pt satisfaction
Ajori, 2012 [41]	170 (130)	Abdominal hysterectomy, adult women	PBO vs Gaba 600mg preop	Reduction of postop pain; opioid, antiemetic consumption at 24h	+	Significant decreases in all measures.
Kinney, 2012 [36]	120	elective thoracotomy, adults	active PBO vs Gaba 600mg preop	Pain scores, opioid consumption, side effects x48h	-	No analgesic benefit
Behdad, 2012 [42]	61	Abdominal hysterectomy, adult women	PBO vs Gaba (100mg 1 day prior, 300mg 2h preop)	Pain, nausea, vomiting, vitals, morphine use	+	Except in the first hour after operation (p = 0.02), there was no significant differences between the two groups in morphine use.

Author, Year [Reference]	n (analyzed)	Population	Intervention	Outcome measure	Results	
Deniz, 2012 [43]	51	Radical retropubic prostatectomy, adult males	Gaba 900mg preop vs none	Opioid consumption, pain scores, rescue analgesia	+	Lower pain scores and reduced rescue analgesia; no difference in opioid consumption.
Ozgencil, 2011 [44]	90	laminectomy and discectomy, adults	PBO vs Gaba 600 vs Pregaba 150mg q12h x2 preop	morphine consumption, pain scores, preop anxiety, pt satisfaction	+	Both gaba and pregaba showed significant positive effects in all measurement categories.
Panah- Khahi, 2011[45]	64	Lower extremity orthopedic surgery, adults	PBO vs 300mg Gaba preop	Pain scores, time to rescue opioid, total opioid consumption	+	Pain scores significantly lower at 2h, no differences later.
